
If dose escalation is completed as planned a maximum of 53 (24 phase 1 and 29 in phase 2) are expected to enroll at a rate of 3 subjects every 1 month for stage I. The first phase of the stage II will recruit 10 subjects at the MTD. If 1 response are seen by 17 weeks on Ruxolitinib, then a total of 29 subjects will be accrued at the MTD to determine efficacy. Maximum accrual is 53 subjects.

Analysis of the following secondary endpoints will be of exploratory nature:

- 1. Acute myeloid leukemia (AML) transformation according to WHO criteria.
- 2. Overall survival (OS).
- 3. Duration of response.
- 4. The Myeloproliferative Neoplasms Symptom Assessment Form (MPN-SAF) at baseline and at best response.
- 5. >50% decrease in splenic length as measured by physical exam
- 6. The suppression of pSTAT5 intracellular signaling after ruxolitinib in CMML subjects (pretreatment, at 1-2hr post treatment, cycle 2, cycle 4, and progression.)
- 7. Determine number of colonies formed in the presence of GM-CSF and/or ruxolitinib (pretreatment and progression) as a future predictor of response.
- 8. Mutational status in our CMML subjects by sanger sequencing of JAK2V617F, c-CBL, N-RAS, K-RAS,RUNX-1, TET2, SRSF2, EZH2, ASXL1, and DNMT3a (pretreatment and progression).
- 9. Mutational status of JAK2 tyrosine kinase at time of progression by deep sequencing of JAK2 to include M929I, Y931C, G935R, R938L, I960V, E985K. (pretreatment and at progression)

Laboratory Correlates

Phases 1 and 2

The pharmacokinetics of ruxolitinib has been extensively studied in subjects with myeloid malignancies. Ruxolitinib is quickly absorbed with peak levels at 1 to 3 hours after ingestion of the tablet. Because of this, subjects will take their first dose of ruxolitinib in the clinic. At that time, and three hours after taking the tablet, peripheral blood will be collected and processed in the lab of [name] in the Stabile Research Building (SRB) at the Moffitt Cancer and Research Institute as described in section 16.

Using processed peripheral blood, pSTAT5 will be measured by flow cytometry at the time of tablet ingestion and 3 hours later. Bone marrow aspirates will also be used to perform colony formation assay as described in section 16 and to collect a minimum of 100 ug of DNA to interrogate the mutational status of the cohort studied as described in section 16.

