6 TREATMENT PLAN

6.1 Ruxolitinib administration

Subjects will not take the morning dose of ruxolitinib at the first regularly scheduled visit. Drug will be administered in the clinic in order to obtain adequate biomarker assessment. On all other days corresponding to study visits, subjects will take the morning dose of study drug prior to the visit, and will note on the subject reminder card the time that medications were taken. Reported adverse events and potential risks are described in Section 11. Appropriate dose modifications for ruxolitinib are described in Section 10. No investigational or commercial agents or therapies other than those described below may be administered with the intent to treat the patient's CMML.

6.1.1 Ruxolitinib will be supplied by INCYTE as tablets that will be self-administered BID orally, with or without food approximately 12 hours apart (morning and night).

6.1.2 The dosage strength is 5 mg/tablet Ruxolitinib phosphate (free base equivalent). Administration instructions will be provided at Study Visits. The administration instructions will state that medication is "For Investigational Use Only". Ruxolitinib 5 mg tablets are packaged as 60 count in high-density polyethylene (HDPE) bottles. The bottles will include labeling "New Drug - Limited by Federal (USA) Law to Investigational Use. The bottles of tablets should be stored at room temperature, 15°C to 30°C (59°F to 86°F). Dose escalation guidelines are detailed below in section 6.5. In phase II of the study, a maximum of 29 subjects will be treated at the MTD identified in phase I.

6.2 **Definition of Dose-Limiting Toxicity**

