- 13.6 **Off study evaluation**: include vital status, date of death/last contact, transformation to AML and the date of transformation to AML if applicable. This evaluation will be updated every 6 month for 2 years.

Study Calendar	Pre- Study	Wk 1	Wk 2	Wk 3	Wk 4	Wk 5	Wk 6	Wk 7	Wk 8	Wk 9	Wk 10	Wk 11	Wk 12	Wk 13	Wk 14	Wk 15	Wk 16	Wk 17	Weeks 18-48 (if response) Monthly visits	Off-Study or continue if responding as per previous weeks
Ruxolitiniba		X	X	X	X	X	X	X	X	X	X	X	X	X	X	X	X	X	X	X
Informed consent	X		1																	
Demographics	X				71											L				
Medical history	X					X				X				X				X	X	X
Physical exam	X					X				X				X				X	X	X
Vital signs	X					X				X				X				X	X	X
Height	X																			X
Weight	X					X				X				X				X	X	
Performance Status	X					X		N.		X				X				X	X	X
Concurrent medication review	X								М											
CBC w/diff,	X	X	X	X	X	X	X	X	X	X	X	X	X	X	X	X	X	X	X	X
Retic Count	X					X				X				X				X		
Serum chemistry ^b	X	X	X	X	X		X		X		X		X		X		X		X	X
INR, PT, and PTT	X							1		7						7				
Adverse event evaluation		X				events v								-						
Bone marrow biopsy/aspirate ^d ***	X			١,					X	•			Ĭ				X			
B-HCG ^c	X				4															
Lab. Correlates	X	X				X				X				X				X		

Prior CMML	X																			
Treatments																				
Transfusion	X					X				X				X				X	X	X
Log																				
Response										X								X	X	X
Assessments															_					
Symptom Score Scale ^f	X	X	X	X	X	X	X	X	X	X	X	X	X	X	X	X	X	X		
Scale ^f																				
Off-treatment																		X	X	X
Assessment/Off																				
-Study Follow-					7															
-Study Follow- up/ CMML Summary Form																				
Summary Form																				

- a. Dose as assigned for cohort in phase 1, dose assigned as MTD in phase 2
- b: Albumin, alkaline phosphatase, total bilirubin, bicarbonate, BUN, calcium, chloride, creatinine, glucose, LDH, potassium, total protein, AST, ALT, sodium, and total bilirubin.
- c: Serum or urine pregnancy test (women of childbearing potential).
- d: in addition to specimen required for pathologic review, and additional aspirate will be collected (goal volume of 30cc)
- e: in addition to specimen required for routine labs, 6 green top vials, 1 red top vial; on week 1, peripheral blood will be collected twice: at time of first dose, and 3 hours after first dose.

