16.1 Sample Collection

At Screening and weeks 1, 5, 9,13, and 17 (see study calendar), peripheral blood will be collected. Designated study personnel will collect the sample from the laboratory draw area. Peripheral blood will be collected in six green top (heparinized) 10cc tubes and one red top (clot activator or no additive) 10cc tube for a total of seven tubes and 70cc of peripheral blood. At the time of the first dose, peripheral blood will be collected twice: once at the time of the first dose (or up to one hour prior to the first dose) in six green top 10 cc tubes and one red top 10 cc tube, and again three hours after the first dose (+/- 30 minutes) in six green top 10 cc tubes and one red top 10 cc tube, for a total of 14 tubes and 140cc of peripheral blood. At Screening and weeks 8 and 16 (see study calendar), bone marrow aspirate will be collected in three lavender (EDTA) 10cc tubes for a total of 30cc. These will be shipped to the H. Lee Moffitt Cancer Center laboratory as directed above within 24hrs and will be processed first by centrifugation (730 rcf for 5 minutes) to collect the supernatant (plasma from green top or lavender top;

serum from red top). Green top and lavender top samples will be additionally processed by centrifugation (530 rcf for 20 minutes) with density gradient medium to collect the mononuclear cellular layer, followed by the addition of RBC lysis buffer to remove RBCs and debris. The mononuclear cells will be cryopreserved as previously described and stored in liquid nitrogen for later use labeled with a unique identifier that corresponds to each patient known only to the investigator and study personnel. The plasma and serum will be cryopreserved for later use labeled with a unique identifier that corresponds to each patient known only to the investigator and study personnel.

16.2 pSTAT5 as a pharmacodynamic marker for ruxolitinib.

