At the time of the first dose the subjects' (may be up to one hour prior to first dose) peripheral blood will be collected, processed and stored as above. Peripheral blood will again be drawn three hours after the first dose (+/- 30 minutes) and be collected, processed and stored as above. Peripheral blood will also be collected at the assigned time points (see study calendar) and processed as above. These samples will be batched for analysis after 10 samples have been processed and cryopreserved. They will be reconstituted in STEM span and 20% FBS in the laboratory of [name]. pSTAT5 will be measured using phos-flow cytometry as previously described at baseline, after one hour of serum free condition, and then stimulated with 0.1, 1, and 10 ng/ml of GM-CSF. The in vitro efficacy of ruxolitinib will also be evaluated by the addition of increasing doses of ruxolitinib and measurement pSTAT5 as above.

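### In the exploratory pSTAT5 endpoint only the week-1 post-dose draw is timed to the dose, so differences from later cycles can reflect hours since dose

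*Combined protocol and SAP*

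**What the plan says.** **Week 1.** Section 6.1 brings the first dose into the clinic: "Drug will be administered in the clinic in order to obtain adequate biomarker assessment". The Laboratory Correlates part of the synopsis gives the reason: "Ruxolitinib is quickly absorbed with peak levels at 1 to 3 hours after ingestion of the tablet". Footnote e of the study calendar (section 13) reads "on week 1, peripheral blood will be collected twice: at time of first dose, and 3 hours after first dose". Sections 16.1 and 16.2 add a tolerance of 30 minutes either way on the second draw, and allow the first to be taken up to an hour before the dose.

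**Later visits.** Section 6.1 states "On all other days corresponding to study visits, subjects will take the morning dose of study drug prior to the visit" and adds that the subject "will note on the subject reminder card the time that medications were taken". Section 16.1 sets the weeks: "At Screening and weeks 1, 5, 9,13, and 17 (see study calendar), peripheral blood will be collected". Section 16.2 says of the later samples only "Peripheral blood will also be collected at the assigned time points (see study calendar) and processed as above". The calendar gives a week for each draw, with a tolerance of a week either way, and no hour.

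**Endpoint and analysis.** Section 3.2.6, repeated in the synopsis and in 15.6.6, lists pSTAT5 suppression before treatment, 1 to 2 h after treatment, at cycle 2, at cycle 4 and at progression. Section 15.6 plans exploratory summaries, mostly in subjects at the MTD, with point estimates and 95% confidence intervals where feasible. It names no model for pSTAT5 and no covariate.

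**The concern.** The protocol's own reasoning is that drug level changes over the first hours after a tablet, and that the biomarker draw must be timed to it. It applies this at one visit and then drops it. From week 5 on, the interval between the home dose and the needle depends on when the subject took the tablet and when the clinic drew blood.

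What is at stake is how one secondary endpoint is read. If pSTAT5 suppression at cycle 2 or cycle 4 looks weaker than in the week-1 post-dose sample, the plan as written cannot tell a real loss of effect from a later draw. Between-subject spread at a given visit has the same ambiguity. Draw times not captured on the day may be unrecoverable afterwards.

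**Working it through.** There is no stated figure to reproduce: the plan attaches no sample size, effect or precision to this endpoint. The check sets the rules side by side and then gives one labelled illustration.

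**1. The sampling rules**

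| | Week-1 post-dose draw | Weeks 5, 9, 13, 17 |
|---|---|---|
| Where the dose is taken | Clinic (6.1) | Before the visit (6.1) |
| Dose time noted | Dose given under observation | Reminder card (6.1) |
| Target interval, dose to draw | 3 h ± 30 min (16.1, 16.2); 1 to 2 h in 3.2.6 and 15.6.6 | None (13, 16.1, 16.2) |
| Draw time required | Implied by the window | Not stated |
| Used in analysis | Not stated (15.6) | Not stated (15.6) |

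The documents do not say which draws stand for cycle 2 and cycle 4. It makes no difference here, because all four later draws follow the same rule.

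**2. What the comparison estimates.** Write S(w, t) for suppression at week w, t hours after the last dose, and t₁ for the week-1 interval. The observed difference splits into two parts:

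S(w, t_w) − S(1, t₁) = [S(w, t₁) − S(1, t₁)] + [S(w, t_w) − S(w, t₁)]

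The first bracket is the change over cycles that objective 1.2.6 wants. The second is draw timing alone. The plan fixes t₁ (in two conflicting ways) and leaves t_w free. It records half of what is needed to compute t_w: the dose time but not the draw time. So the second bracket is neither held at zero nor estimable from what the plan requires.

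**3. Illustration for drug level, not pSTAT5.** Assumptions, none from the documents: mono-exponential decline from 3 h on, half-life h of 2 to 6 h, no carry-over from earlier doses. Level relative to the 3 h level is R(t) = 2^(−(t−3)/h). For example, at t = 8 and h = 2, R = 2^(−2.5) = 0.18; at t = 8 and h = 6, R = 2^(−5/6) = 0.56.

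| Hours after dose | h = 2 | h = 3 | h = 4 | h = 6 |
|---|---|---|---|---|
| 2.5 | 1.19 | 1.12 | 1.09 | 1.06 |
| 3.5 | 0.84 | 0.89 | 0.92 | 0.94 |
| 5 | 0.50 | 0.63 | 0.71 | 0.79 |
| 6 | 0.35 | 0.50 | 0.59 | 0.71 |
| 8 | 0.18 | 0.31 | 0.42 | 0.56 |

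Under these assumptions the 30-minute tolerance keeps drug level within 0.84 to 1.19 of its 3 h value at worst, while a draw at 5 to 8 h sits at 0.18 to 0.79 of it. This shows only that an untimed draw can matter. It does not say that later draws fall at 5 to 8 h, and it does not convert to a change in pSTAT5.

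**4. Direction.** Later draws could also fall earlier than the week-1 interval. The documents fix neither sign nor size. A tendency toward longer intervals would look like lost suppression.

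**5. Samples with no same-day dose.** Section 7 sets 16 weeks of treatment, with an end-of-study visit at week 17 for those who do not continue. A week-17 sample from such a subject, or a progression sample taken after stopping, may be off drug altogether.

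**The case against.** The strongest reply is that this is one exploratory biomarker (section 1.2 and 15.6 say so) in at most 29 phase 2 subjects, and that the assay may blunt any timing effect. Samples may take up to 24 hours to ship. Cells are then separated and frozen, and later thawed, measured, held serum-free for an hour and stimulated with GM-CSF. Nothing in the documents shows how far that readout follows drug level at the moment of the draw. This stands, and it is why no effect size can be claimed. It does not remove the gap: section 16.2 treats pSTAT5 as a pharmacodynamic marker and times the first draw accordingly, so the plan itself assumes that a dose-related signal survives.

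It is also fair that the dose time is already on the reminder card. With draw times added, the interval could be computed. That makes the remedy small, but the plan neither asks for the draw time nor uses the interval.

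Timing is not the only difference from week 1, either. Phase 2 dose reductions (10.2) and the switch to once-daily dosing with CYP3A4 inhibitors (10.3) also separate later samples from the first. Fixing the draw time leaves those in place.

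A reader might infer more than the documents support:

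- **That the resistance work is compromised.** Section 16.5 sequences JAK2 from DNA and uses no pSTAT5 result. Draw timing cannot change a mutation call.
- **That a correlation of suppression with response is weakened.** The listed response correlations concern in vitro activity (1.2.7) and mutations (1.2.8). No objective relates on-treatment suppression to response.
- **That the drug-level ratios above measure the bias.** They rest on an assumed half-life and assumed draw times, and they concern drug level only.

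**Conclusion.** The gap is real and confined to the exploratory pSTAT5 endpoint. Following the plan as written yields a week-1 sample with a defined interval after dose and later samples without one, so the comparison across cycles mixes hours since dose with change in suppression. This conclusion needs only the plan's own premise that the marker responds to drug level, which varies with time since the tablet. Its size and direction cannot be derived from the documents.

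The MTD, the response endpoint, the sample size, the error rates and the safety decisions are untouched. This is a cheap improvement worth making before more samples are collected, not a flaw in the trial's main conclusions. Separately, the 1 to 2 h in the endpoint lists (synopsis, 3.2.6, 15.6.6) conflicts with the 3 h in the synopsis laboratory text, calendar footnote e, 16.1 and 16.2. These passages must be reconciled, because the week-1 interval is the reference for everything later.

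**What to change.** - **Reconcile** the week-1 post-dose interval across the endpoint lists, the synopsis, the calendar and 16.1/16.2.
- **16.1 and 16.2:** record the clock time of every on-treatment draw. Schedule the draws at weeks 5, 9, 13 and 17 to the same post-dose window as the reconciled week-1 time, counted from the dose time on the reminder card.
- **15.6.6:** report hours since last dose with each pSTAT5 value. Use in-window draws as the main comparison with week 1. Show all draws, adjusted for or stratified by hours since dose, as support; with few subjects, stratified display is enough. Flag samples with no same-day dose, such as week 17 after treatment has ended, or progression.

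No dose, dosing schedule or sample size changes. The cost is one data field, a short addition to the analysis section, and some coordination of home dose, travel and clinic slot. A few out-of-window draws would leave the main summary but stay in the supporting one. If the scheduling proves impractical, recording the draw time and reporting the interval still makes the timing visible.

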6.3 Definition of Maximum Tolerated Dose

The maximum tolerated dose (MTD) is defined as the highest dose where < 33% of subjects experience DLT.

Dose Escalation Scheme

In phase 1 of this study, subjects will be allocated to starting doses (10 mg/d to be escalated up to 40mg/d, which is outlined in the table above). The second phase of the study (phase 2) will enroll a maximum of 29 subjects at the MTD determined in phase 1. In each cohort in the phase I study, up to 6 subjects will be enrolled. Based on whether DLTs are observed during 8 weeks of treatment, the dose for the subsequent cohort will be determined. If no DLT is observed during an 8 week period then another 6 subjects will be enrolled at the next dose level (see section 6.2.1 table). If 1 DLT is observed after three subjects are enrolled then dose escalation will continue at the same dose level until 6 total patients are enrolled. If a total 1 of 6 subjects enrolled experience at DLT after all subjects have had an 8 week monitoring period then dose escalation can proceed. If 2 or more of 6 total subjects experience a DLT then dose escalation is complete and the MTD will be the antecedent dose level. Dose escalation will proceed according to the following scheme. Dose-limiting toxicity (DLT) is defined above.

6.3.1 Dose Escalation Rules of Rolling Six Design

Cohort	-	DLT D	Enrolling Dose level	
No.	No.	No. without	No. with Pending	MTD Not Exceeded
Enrolled	DLTs	DLT	Data	
2	0,1	Any	Any	n

2	2	0	0	n-1
3	0	0,1,2	3,2,1	n
3	0	3	0	n+1
3	1	0,1	2,1	n
3	1	2	0	n
3	>1	Any	Any	n-1
4	0	0,1,2	4,3,2	n
4	0	3	1	n
4	0	4	0	n+1
4	1	0,1	3,2	n
4	1	2	1	n
4	1	3	1	n
4	>1	Any	Any	n-1
5	0	0,1,2	5,4,3	n
5	0	3,4	2,1	n
5	0	5	0	n+1
5	1	0,1	4,3	n
5	1	2	2	n
5	1	3,4	1,0	n
5	>1	Any	Any	n-1
6	0	0,1,2	6,5,4	Suspend
6	0	3,4	3,2	Suspend
6	0	5,6	1,0	n+1
6	1	0,1	5,4	Suspend
6	1	2	3	Suspend
6	1	3,4	2,1	Suspend
6	1	5	0	n+1
6	>1	Any	Any	n-1
			1 501 11	

Adapted from Skolnik, et al. Shortening the Timeline of Pediatric Phase I Trials: The Rolling Six Design. JCO 2008 n=current dose level. n+1=dose escalation. n-1=dose de-escalation. Pending data=less than 8 weeks of follow-up data.

6.4 General Concomitant Medication and Supportive Care Guidelines

All concomitant medications and medication history for 2 weeks MUST be recorded in the eCRF, and include: drug name, dose, frequency of administration, start and stop dates, and indication. All prior medications used to treat CMML will be recorded regardless of when they were received by the subject. Information collected for these medications will include dates of use, best treatment response (eg, disease improvement, stabilization of disease or no improvement/disease progression), and reasons for stopping therapy. Any change in dosage of any concomitant medication (change in dose or frequency) MUST be recorded in the eCRF, to include: drug name, dose, frequency of administration, start and stop dates and indication.

6.5 **Permitted Medications**

6.5.1.1 Growth Factors

Erythropoiesis-stimulating agents (ESAs) are allowed for anemia during the study as per accepted standards in the treatment of CMML as long as the ESA was initiated >8 weeks prior to the first dose of ruxolitinib. Subjects who enter the study on ESAs should continue at the same dose schedule until the optimal dose of study medication has been established. G-CSF is allowed during the study for subjects with severe neutropenia and recurrent infections. Subjects who enter the study on G-CSF should continue at the same dose schedule until the optimal dose of study medication has been established. GM-CSF is not permitted at any time during the study as preclinical evidence suggests that GM-CSF may be important for CMML proliferation and survival.

6.5.1.2 Systemic corticosteroids

Systemic corticosteroid doses greater than the equivalent of 10 mg prednisolone per day is not permitted, unless use is part of an ruxolitinib-dose tapering strategy. (see section 7 Optional Dose Tapering Strategy).

6.5.1.3 Aspirin

Aspirin in doses exceeding 162 mg per day is not permitted. Low dose aspirin (≤ 162 mg/day) and non steroidal anti-inflammatory agents (acetaminophen, Ibuprofen) may be used.

6.5.1.4 Medications that are inhibitors of CYP3A4

When concomitant administration of a potent systemic inhibitor of CYP3A4 metabolizing enzymes (ketoconazole, clarithromycin, itraconazole, nefazodone and telithromycin, see section 7) that is required for subject management, the dose of ruxolitinib tablets must be adjusted as described in section 7. Based on the low overall bioavailability of topical ketoconazole, with very low systemic levels seen following topical administration, no dose adjustment of ruxolitinib is needed for use with topical ketoconazole.

6.5.1.5 Blood Products

The use of blood products to include packed red blood cells (PRBCs) and platelet transfusions are permitted and to be given at the discretion of the

treating physician. Recommended guidelines for transfusion include a platelet threshold of 10,000/L for platelet transfusion and a hemoglobin threshold of 8g/dL for PRBC transfusion.

6.6 Prohibited Medications

Subjects must abstain from using prohibited prescription or non-prescription drugs within 7 days or 5 half-lives (whichever is longer) prior to the first dose of study medication and until completion of follow-up procedures (Exclusion Criteria). The following medications are prohibited during the study:

- Any prior or concomitant use of another JAK inhibitor.
- Any investigational medication other than the study drugs.
- Use of the potent inducers of CYP3A4, rifampin and St John's Wart, is not permitted at any time during participation in the study.
- The GM-CSF growth factor receptor agonists must not be used. Preclinical evidence suggest that it is important for CMML proliferation and survival and it is directly upstream for JAK2, the target of ruxolitinib. GM-CSF must not have been used for at least 28 days prior to receiving the first dose of study drug.

7 **Duration of Therapy**

Subjects will be treated for a total of 16 weeks. For subjects responding at week 16, treatment may continue until one of the following criteria applies:

- 7.1 Dose-limiting toxicity is reached,
- 7.2 Inter-current illness that prevents further administration of treatment,
- 7.3 Unacceptable adverse event(s),
- 7.4 Patient decides to withdraw from the study, or
- 7.5 General or specific changes in the patient's condition render the patient unacceptable for further treatment in the judgment of the investigator.
- 7.6 Evidence of disease progression by the IWG 2006 criteria.

Subjects who wish not to continue treatment will complete their end of study visit at week 17. Subjects who were not enrolled in the MTD cohort can increase to the MTD after week 17 if the participant still meets the eligibility criteria. Responding patients will be able to continue until marketing approval of ruxolitinib for CMML.

8 Duration of Follow-Up

Subjects will be followed as per calendar on treatment for 17 weeks. After 17 weeks patient who continue on study will be followed monthly. Off study data on AML transformation and overall survival will be updated every 6 month or until death, whichever occurs first. Subjects removed from study for unacceptable adverse events will be followed until resolution or stabilization of the adverse event.

9 Criteria for Removal from Study

